sponsored multi-center, non-randomized Phase Ib trial (KN 012) showed that single agent pembrolizumab given at 10 mg/kg Q2W is a well-tolerated and effective treatment with significant therapeutic activity in a subset of heavily pre-treated patients with mTNBC.

Methods: PD-L1 expression in $\geq 1\%$ tumor cells or in stroma [i.e., PD-L1 (+) mTNBC] was required for study entry. Tumor PD-L1 status was determined by immunohistochemical analysis of archival tumor specimens using the Merck proprietary 22C3 antibody. Primary objectives of this study were to determine the safety, tolerability, and antitumor activity of pembrolizumab in patients with PD-L1 (+) mTNBC. Secondary objectives included assessments of progression-free survival (PFS), overall survival (OS), and duration of response (DOR). Adverse events (AEs) reported in any patient receiving at least 1 dose of study treatment were monitored and graded using National Cancer Institute Common Terminology Criteria for Adverse Events version 4.0 (NCI CTCAE v. 4.0). Radiographic imaging was obtained every 8 weeks and evaluated by both investigator and an independent radiologist to assess clinical responses as defined by RECIST 1.1.

Results: A total of 32 female patients with a median age of 50.5 years (range 29-72 years) and PD-L1 (+) mTNBC were enrolled in the study. Most of these patients had received and progressed on multiple lines of therapy for advanced disease (the median number of prior treatments in the metastatic setting was 3). According to data through 06-Nov-2014, five patients (15.6%) experienced at least one drug-related serious adverse event (SAE); each of four patients experienced one of the following: Grade 3 anemia, headache, aseptic meningitis or pyrexia, and a fifth patient experienced Grade 5 disseminated intravascular coagulation (DIC) with thrombocytopenia and decreased blood fibrinogen. Of the 27 patients with centrally confirmed measurable disease, one patient (3.7%) had a complete response (CR), 4 patients (14.8%) had a confirmed partial response (PR), 25.9% had stable disease (SD), and 44.4% had progressive disease (PD), as assessed by the central imaging vendor. As of 06-Nov-2014, the median duration of response had not been reached (range 15 to 40+ weeks), and three patients (1 CR; 2 PR) were still on treatment after at least 11 months.

KN 086: Subjects receiving pembrolizumab as 2L+ monotherapy for mTNBC (Cohorts A and C)

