8.2.3.1 Efficacy Endpoints

The primary efficacy endpoint is objective response rate (ORR), defined as the proportion of subjects in the analysis population who have complete response (CR) or partial response (PR), based on RECIST 1.1 by the central imaging vendor at any time during the study. As supportive analyses, ORR will also be evaluated by a) site investigator and local radiology review based on RECIST 1.1 and b) irRECIST by the central imaging vendor.

Secondary efficacy endpoints include:

- Duration of response (DOR), defined as the time from first documented evidence of CR or PR until disease progression or death due to any cause, whichever occurs first, for subjects who demonstrate CR or PR, based on RECIST 1.1 by the central imaging vendor.
- Disease control rate (DCR), defined as the percentage of subjects who have achieved confirmed CR or PR or have demonstrated SD for at least 24 weeks prior to any evidence of progression, based on RECIST 1.1 by the central imaging vendor.
- Progression-free survival (PFS), defined as the time from first dose of study medication to the first documented disease progression or death due to any cause, whichever comes first, based on RECIST 1.1 by the central imaging vendor.

- Overall survival (OS), defined as the time from first dose of study medication to death due to any cause.

As exploratory endpoints, DOR and DCR and PFS will also be evaluated based on a) RECIST 1.1 by study site and local radiology review and b) irRECIST by the central imaging vendor.

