8.2.4 Analysis Populations

8.2.4.1 Efficacy Analysis Populations

The All-Subjects-as-Treated (ASaT) population, which consists of all enrolled subjects who receive at least one dose of study medication with measurable metastatic disease at baseline, will serve as the primary population for the analyses of efficacy data in this trial.

Details on the approach to handling missing data for efficacy analyses are provided in Section 8.2.5 Statistical Methods.

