8.2.5 Statistical Methods

8.2.5.1 Statistical Methods for Efficacy Analyses

Efficacy of pembrolizumab as 2L+ monotherapy for mTNBC will be evaluated primarily in PD-L1 (+) and overall population (all comers) in Cohort A, and also in subjects with PD-L1 strong (+) tumors from Cohorts A and C combined. Cohort A will be evaluated for association between PD-L1 biomarker expression and antitumor activity. A separate biomarker SAP will be devoted to association between PD-L1 biomarker expression and antitumor activity analysis.

The primary efficacy endpoints are ORR based on RECIST 1.1 by the central imaging vendor in subjects with PD-L1 (+) mTNBC of Cohorts A, overall population (all comers) of Cohort A and in subjects with PD-L1 strong (+) mTNBC. The point estimate 95% Agresti-Coull (A-C) confidence interval (CI) (as determined by the upper and lower 97.5% one-sided confidence bounds) will be provided based on normal approximation for the binomial distribution. Subjects without response data will be counted as non-responders.

Similarly, a supportive analysis to the primary method, ORR based on RECIST 1.1 by study site investigator and local radiology review will also be performed in the same fashion.

For the secondary endpoint of DCR, similar estimation methods used for ORR will be applied.

For DOR, PFS and OS, Kaplan-Meier (KM) curves, median estimates, and survival at 6 and 12 months based on the KM curves (95% CI is based on Greenwood's formula) will be provided as appropriate. Subjects without efficacy evaluation data or without survival data will be censored at Day 1. The restricted mean survival time (RMST) for DOR will also be provided as a supportive analysis.

Censoring rules for DOR are summarized in [Table 9](#).

Table 9 Censoring Rules for DOR

Situation	Date of progression or censoring	Outcome
No progression nor death, no new anti-cancer therapy initiated	Last adequate assessment	Censor (non-event)
No progression nor death, new anti-cancer therapy initiated	Last adequate assessment before new anti-cancer therapy initiated	Censor (non-event)
≥ 2 consecutive missed adequate disease assessments	Last adequate assessment prior to ≥ 2 missed adequate disease assessments	Censor (non-event)
Death or progression after ≤ 1 missed adequate disease assessments	Death or progression	End of response (Event)

A missed disease assessment includes any assessment that is not obtained or is considered inadequate for evaluation of response.

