Similar estimation methods will be applied to the efficacy analyses for the subjects with PD-L1 (+) mTNBC in Cohort B.

[Table 10](#) summarizes the key efficacy analyses for primary and secondary endpoints in this study.

Table 10 Analysis Strategy for Primary/Secondary Efficacy Endpoints in Cohorts A and C

Endpoint/Variable (Description, Time Point)	Statistical Method	Analysis Population	Missing Data Approach
Primary:			
ORR, based on RECIST1.1 by the central imaging vendor	95% Agresti-Coull CI	ASaT - PD-L1 (+) - overall - PD-L1 strong (+)	Subjects with missing data are considered non-responders
Secondary:			
Response duration (DOR) Based on RECIST1.1 
 o by the central imaging vendor o by study site investigator and local radiology review 	Summary statistics using Kaplan-Meier method	All responders - PD-L1 (+) - overall - PD-L1 strong (+)	Non-responders are excluded in analysis
ORR Based on RECIST1.1 
 o by study site investigator and local radiology review 	Agresti-Coull 95% CI	ASaT - PD-L1 (+) - overall - PD-L1 strong (+)	Subjects with missing data are considered non-responders
DCR Based on RECIST1.1 
 o by the central imaging vendor o by study site investigator and local radiology review 	Agresti-Coull 95% CI	ASaT - PD-L1 (+) - overall - PD-L1 strong (+)	Subjects with missing data are considered non-responders
Progression-free survival (PFS) Based on RECIST1.1 
 o by the central imaging vendor o by study site investigator and local radiology review 	Summary statistics using Kaplan-Meier method	ASaT - PD-L1 (+) - overall - PD-L1 strong (+)	Censored at last assessment
Overall survival (OS)	Summary statistics using Kaplan-Meier method	ASaT - PD-L1 (+) - overall - PD-L1 strong (+)	Censored at last assessment
95% confidence interval is determined by the upper and lower 97.5% one-sided confidence bounds.			

Similar efficacy methods will be applied to Cohort B for subjects with PD-L1 (+) tumors receiving pembrolizumab as 1L monotherapy for mTNBC.

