8.2.6 Multiplicity

This is an estimation study. The estimation of ORR and associated 95% confidence intervals of ORR will be provided. No multiplicity adjustment will be applied in subjects with PD-L1 (+) mTNBC of Cohorts A, overall population (all comers) of Cohort A and in subjects with PD-L1 strong (+) mTNBC.

There are also no hypotheses for other parameters of DOR, DCR, PFS, and OS or for Cohort B.

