3.6 Statistical Methods

3.6.1 Statistical Methods for Efficacy Analyses

Efficacy of pembrolizumab as 2L+ monotherapy for mTNBC will be evaluated primarily in PD-L1 (+) and overall population (all comers) in Cohort A, and also in subjects with PD-L1 strong (+) tumors from Cohorts A and C combined. Cohort A will be evaluated for association between PD-L1 biomarker expression and antitumor activity.

The primary efficacy endpoints are ORR based on RECIST 1.1 by the central imaging vendor in subjects with PD-L1 (+) mTNBC of Cohorts A, overall population (all comers) of Cohort A and in subjects with PD-L1 strong (+) mTNBC. The point estimate, 95% Agresti-Coull confidence interval (as determined by the upper and lower 97.5% one-sided confidence bounds) will be provided based on normal approximation for the binomial distribution. Subjects without response data will be counted as non-responders.

Similarly, a supportive analysis to the primary method, ORR based on RECIST 1.1 by study site investigator and local radiology review will also be performed in the same fashion.

For the secondary endpoint of DCR, similar estimation methods used for ORR will be applied.

For the secondary endpoint of DOR, the definitions are the following:

For subjects who demonstrate CR or PR, duration of response is defined as the time from first documented evidence of CR or PR until disease progression or death due to any cause, whichever occurs first.

Subjects who are alive, have not progressed, have not initiated new anti-cancer treatment, and have not been determined to be lost to follow-up are considered ongoing responders at the time of analysis.

Censoring rules for DOR are summarized in [Table 1](#).

Table 1 Censoring Rules for DOR

Situation	Date of Progression or Censoring	Outcome
No progression nor death, no new anti-cancer therapy initiated	Last adequate disease assessment	Censor (non-event)
No progression nor death, new anti-cancer therapy initiated	Last adequate disease assessment before new anti-cancer therapy initiated	Censor (non-event)
after ≥ 2 missed adequate disease assessments	Last adequate disease assessment prior to the after ≥ 2 missed adequate disease assessments	Censor (non-event)
Death or progression after ≤ 1 missed adequate disease assessments	PD or death	End of response (Event)
A missed disease assessment includes any assessment that is not obtained or is considered inadequate for evaluation of response.		

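### The Day-1 censoring sentence has no exception for a recorded death, so as written it censors a death without a post-baseline scan at time zero for PFS, against the PFS definition

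*Combined protocol and SAP*

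**What the plan says.** Protocol section 8.2.5.1 introduces the Kaplan-Meier analyses of DOR, PFS and OS in one sentence. The next sentence is "Subjects without efficacy evaluation data or without survival data will be censored at Day 1". Supplemental SAP (sSAP) section 3.6.1 carries it unchanged.

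Protocol section 8.2.3.1 and sSAP section 3.4.1 define PFS as the "time from first dose of study medication to the first documented disease progression or death due to any cause". Neither definition asks for a scan before a death counts.

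The efficacy population in section 8.2.4.1 is "all enrolled subjects who receive at least one dose of study medication with measurable metastatic disease at baseline". A post-baseline scan is not a condition of entry, so a treated subject who dies early is in the analysis set.

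Two other places deal with censoring:

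- Protocol Table 9 and sSAP Table 1 contain a row that makes death an event, but both tables are limited to duration of response ("Censoring rules for DOR are summarized in" Table 1, in the sSAP's words).
- Protocol Table 10 and sSAP Table 2 give only "Censored at last assessment" as the missing-data approach for PFS and OS.

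**The concern.** The definition counts a death without a scan as a PFS event, and the censoring sentence takes the same subject out of the risk set before any event can occur. A programmer who follows the definition and one who follows the censoring sentence will draw different PFS curves, and each can cite the plan.

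The sentence as written errs in the favourable direction, because it removes the earliest failures. PFS is a key secondary endpoint, there is no control arm to share the bias, and Kaplan-Meier estimates at 6 and 12 months are planned. The first scheduled scan is at 9 weeks, in a 2L+ population for which section 4.2.1 cites a median PFS of 2-3 months and a median OS of 9-12 months. Some deaths before the first scan are therefore to be expected.

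**Working it through.** No figure in the plan depends on this rule, so there is none to reproduce. The check is a reading of the text, then an illustration of size.

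**Step 1: one subject under each reading.** Take a subject who receives one dose and dies on day 40 with no post-baseline scan. By the PFS definition this is an event at day 40. Under the Day-1 sentence:

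| Reading of the sentence | PFS result |
|---|---|
| Strict *or*: either gap triggers censoring | Censored at Day 1 |
| Respective: evaluation data for DOR/PFS, survival data for OS | Censored at Day 1 |
| A recorded death itself counts as efficacy evaluation data | Event at day 40 |

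Only the third reading agrees with the definition, and neither document states it. Table 10's entry does not help, because this subject has no post-baseline assessment to be censored at, and the entry does not say that the death counts.

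**Step 2: effect on the curve.** Suppose k of N subjects are event-free at time t, a share f died earlier without a scan, and there is no other censoring.

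- Deaths counted as events: S(t) = k/N.
- Rule as written: the fN subjects leave the risk set at time zero, so the estimate is k/(N - fN) = S(t)/(1-f).
- Gain = S(t) × f/(1-f), always upward.

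A product-limit calculation with N=160 confirmed this. With 8 such deaths, and the rest exponential with a median PFS of 2.5 months, 6-month PFS was 29/160 = 18.1% with deaths as events and 29/152 = 19.1% under the rule, a ratio of 1.053 = 1/(1-0.05).

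**Step 3: size at 6 months.** The documents do not give f, so 2%, 5% and 11% are assumptions. Taking the 2-3 month median PFS in section 4.2.1 as exponential (also an assumption), S(6) is 0.5^(6/2) = 12.5% to 0.5^(6/3) = 25%.

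| Assumed f | Subjects of 160 | Factor 1/(1-f) | 12.5% becomes | 25% becomes |
|---|---|---|---|---|
| 2% | about 3 | 1.02 | 12.8% (+0.3) | 25.5% (+0.5) |
| 5% | 8 | 1.05 | 13.2% (+0.7) | 26.3% (+1.3) |
| 11% | about 18 | 1.12 | 14.0% (+1.5) | 28.1% (+3.1) |

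For scale, the 95% CI half-width at N=160 is 1.96 × √(0.125 × 0.875/160) = 5.1 points to 1.96 × √(0.25 × 0.75/160) = 6.7 points.

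**Step 4: is an f of this order conceivable?** This is an illustration, not a bound. The first scan is due at 63 ± 7 days. With a constant hazard and a median OS of 9-12 months:

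- Day 63 (2.07 months): 1 - exp(-ln2 × 2.07/12) = 11.3%; with a 9-month median, 14.7%.
- Day 70 (2.30 months): 12.4% and 16.2%.

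So about 11-16% would die by the first scan window. Those who were scanned before death do not count towards f.

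I make no claim about median PFS. In the N=160 check with 8 deaths it moved from 2.29 to 2.48 months with continuous progression times, but stayed at 4.14 months when progression was recorded only at 9-weekly scans.

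**The case against.** The best defence is that this is a missing-data rule. Section 8.2.4.1 sends the reader to section 8.2.5 for the handling of missing data, and a subject with a recorded death is not missing a PFS outcome. On that view, events count and only subjects with nothing recorded go to Day 1. The sponsor may well have meant this. What stands is that efficacy evaluation data is an undefined term, so equating it with a post-baseline tumour assessment is itself an interpretation. But the alternatives are also unwritten. Counting the baseline scan as evaluation data would leave that half of the sentence almost nobody to apply to, because measurable disease on central imaging is required for entry. The sponsor did write a death-is-an-event row for DOR and wrote none for PFS.

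The objection on materiality also stands. PFS carries no hypothesis ("There are also no hypotheses for other parameters of DOR, DCR, PFS, and OS or for Cohort B"), and every gain in step 3 is below the half-width at N=160. For the 55 PD-L1 strong (+) subjects the half-width is wider still, 8.7-11.4 points by the same formula.

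A reader might infer more than the documents support:

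- *That OS deaths are lost as well.* The strict *or* would do this, but it defeats the OS definition ("time from first dose of study medication to death due to any cause") and the survival follow-up in sections 7.1.5.3.4 and 7.1.5.4. The respective reading is the natural one for OS, so a clarification is enough.
- *That 11-16% is a ceiling or an estimate of f.* It rests on a constant hazard and on a median for 2L+ patients in general. This trial requires ECOG 0-1 and excludes CNS metastases, which would lower it; missed scans would raise f.
- *That the earlier pembrolizumab study shows f.* Section 4.2.1 reports 1 CR, 4 PR and "25.9% had stable disease (SD), and 44.4% had progressive disease (PD), as assessed by the central imaging vendor". That is 1 + 4 + 7 + 12 = 24 of 27, but no reason is given for the other 3, so they say nothing firm about deaths.
- *That unscheduled scans make the group negligible.* In section 7.1.2.6.2 the allowance for more frequent imaging attaches to scans after the first. The discontinuation scan in the flow chart will reduce the group, by an unknown amount.

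**Conclusion.** The concern holds for PFS. As written, the Day-1 sentence contradicts the PFS definition for a treated subject who dies without a post-baseline tumour assessment, and nothing in either document resolves it. The error is one-sided: after the early deaths PFS is inflated by 1/(1-f). With f assumed at 2-11% and 6-month PFS at 12.5-25%, that is about 0.3 to 3.1 points; the true f is unknown.

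The consequence is limited. ORR and DCR already count subjects with missing data as non-responders, DOR includes only responders (who have a scan by definition), and neither the sample-size tables nor the two interim rules use PFS. The point is worth correcting because it biases a key secondary estimate in the favourable direction and is easy to remove. It does not call the primary analysis into question.

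**What to change.** In protocol section 8.2.5.1 and sSAP section 3.6.1, replace the sentence with wording to this effect:

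*For PFS, a death without a post-baseline tumour assessment is an event on the date of death. Day-1 censoring applies only to subjects with neither a post-baseline tumour assessment nor a recorded death. For OS, a recorded death is always an event.*

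Align the PFS entries in Table 10 and sSAP Table 2 with this, and report the number of subjects in each group (deaths without a scan; neither scan nor death). If the sponsor also rewords the OS censoring date, the OS entries in both tables must change to match. How to treat a PFS death or progression after two or more missed assessments is a separate choice that the plan leaves open; the sponsor may wish to settle it in the same edit.

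The cost is a few sentences and a table entry in each document, plus one extra line in the PFS output. If the sponsor always intended this, no result changes. If not, PFS may read slightly less favourably.

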8.2.5.2 Statistical Methods for Safety Analyses

Safety and tolerability will be assessed by clinical review of all relevant parameters including adverse experiences (AEs), laboratory tests, and vital signs by cohort and total (combining across Cohorts A-C). Summary statistics (counts, percentage, mean, standard deviation, etc.) will be provided for the safety endpoints as appropriate. The confidence interval for the

incidence rate of Grade 2 or higher adverse events with an immune etiology and the incidence rate of Grade 4/5 AEs will be provided as appropriate.

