3.0 OBJECTIVE(S) & HYPOTHESIS(ES)

3.1 Primary Objective(s) & Hypothesis(es)

1. **Objective (Cohort A):** To estimate the Objective Response Rate (ORR) to pembrolizumab as 2L+ monotherapy for PD-L1 (+) centrally confirmed mTNBC and centrally confirmed mTNBC independent of PD-L1 status (all comers), based on RECIST 1.1 as assessed by the central imaging vendor.
2. **Objective (Cohorts A+C):** To estimate the ORR to pembrolizumab as 2L+ monotherapy in subjects with PD-L1 strong (+) centrally confirmed mTNBC, based on RECIST 1.1 as assessed by the central imaging vendor.
3. **Objective (Cohorts A-C):** To determine the safety and tolerability of pembrolizumab monotherapy for mTNBC across cohorts and by PD-L1 status within lines of treatment for mTNBC.

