8.1 Statistical Analysis Plan Summary

This section contains a brief summary of the statistical analyses for this trial. Full detail is in the Statistical Analysis Plan (SAP) (Section 8.2).

In addition, a separate analysis plan document will be issued prior to biomarker unblinding for each of the following laboratory procedures and assessments: (1) Biomarkers (detailed in Section 7.1.3.4 and 7.1.3.5) and their association with antitumor efficacy and (2) Pharmacokinetic and pharmacodynamics evaluation (detailed in Section 7.1.3.3)

Study Design Overview	A Phase II Clinical Trial of Pembrolizumab as Monotherapy in Subjects with Metastatic Triple-Negative Breast Cancer (mTNBC)
Treatment Assignment	Treatment assignment is open label.
Analysis Populations	Efficacy: All Subjects as Treated (ASaT) Safety: All Subjects as Treated (ASaT)
Primary Endpoint(s)	Objective Response Rate (ORR)
Statistical Methods for Key	ORR estimation

Efficacy Analyses	
 • 2L+ population 
 ○ PD-L1 (+) population (Cohort A) ○ Overall population (Cohort A) ○ PD-L1 strong (+) population (Cohorts A+C) • 1L population (Cohort B) • Counts and percentages • 95% Agresti-Coull confidence intervals
Statistical Methods for Key Safety Analyses	Counts and percentages of AEs will be provided. Confidence intervals for rates of AEs of clinical interest will be computed using the exact binomial method.
Interim Analyses	
 • Futility analysis for 2L+ subjects (Cohort A) with PD-L1 (-) tumors based on no progression 
 ○ ~25 PD-L1 (-) subjects ○ If no response or stable disease, continue 2L+ population (Cohort A) in PD-L1 (+) patients only • Evaluation of expansion to Cohort C for PD-L1 strong (+) population based on ORR. 
 ○ ~10 patients evaluable through response, progression or 18-week scan, whichever comes first. ○ Cohort C may start if ≥ 1 responses observed 
The final analysis of Cohorts A and C combined is to be completed when subjects are evaluable through response, progression or 18-week scan, whichever comes first.

Multiplicity	This is an estimation study. No multiplicity adjustment will be applied.

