	17	15.5%	(9.8,23.5)
	18	16.4%	(10.5, 24.5)
	22	20.0%	(13.5,28.5)
135	14	10.4%	(6.2,16.8)
	21	15.6%	(10.3,22.7)
	27	20.0%	(14.1,27.6)
160	16	10.0%	(6.2,15.7)
	24	15.0%	(10.2,21.4)
	32	20.0%	(14.5,26.9)
170	17	10.0%	(6.3,15.5)
	26	15.3%	(10.6,21.5)
	34	20.0%	(14.6,26.7)
180	18	10.0%	(6.3,15.3)
	27	15.0%	(10.5,21.0)
	36	20.0%	(14.8,26.5)

ORR in PD-L1 strong (+) in Cohorts A + C

There will be ~55 subjects with PD-L1 strong (+) tumors enrolled in Cohort A and Cohort C.

Table 13 shows the two-sided 95% A-C CI of ORR with 55 evaluable subjects for different observed response rates. With 55 subjects with PD-L1 strong (+) tumors, if there are at least 11 responders observed, the lower bound of the 95% A-C CI for ORR will be above 10%.

Table 13 Two-sided 95% A-C CI of ORR with 55 Evaluable Subjects

Number of Observed Responders	ORR Estimates	95% A-C CI of ORR (%)
6	10.9%	(4.7,22.2)
8	14.5%	(7.3,26.4)
9	16.4%	(8.6,28.5)
10	18.2%	(10.0,30.5)
11	20.0%	(11.4,32.5)
13	23.6%	(14.2,36.5)
14	25.5%	(15.7,38.4)

Table 14 shows the Two-sided exact 95% CI of AE Rate with 55 subjects.

Table 14 Two-sided 95% Exact CI of AE Incidence Rate with 55 Evaluable Subjects

Number of AE	AE Incidence Rate Estimates	95% CI of Incidence Rate (%)
6	10.9%	(4.1,22.2)
11	20.0%	(10.4,33.0)
17	30.9%	(19.1,44.8)
22	40.0%	(27.0,54.1)
28	50.9%	(37.1,64.6)

ORR in PD-L1 (+) Cohort B

There will be ~80 subjects with PD-L1 (+) tumors enrolled in Cohort B.

Table 15 shows the two-sided 95% CI of ORR with 80 or 100 subjects for different observed response rates.

Table 15 Two-sided 95% A-C CI of ORR with 80 or 100 Subjects

Sample Size (N)	Number of Observed Responders	ORR Estimates	95% CI of ORR (%)
80	12	15%	(8.6,24.6)
	16	20%	(12.6,30.1)
	20	25%	(16.7,35.6)
	24	30%	(21.0,40.8)
	28	35%	(25.4,45.9)
	32	40%	(30.0,51.0)
	36	45%	(34.6,55.9)
100	15	15%	(9.2,23.4)
	20	20%	(13.3,29.0)
	25	25%	(17.5,34.4)
	30	30%	(21.9,39.6)
	35	35%	(26.3,44.8)
	40	40%	(30.9,49.8)
	45	45%	(35.6,54.8)

Table 16 shows the Two-sided exact 95% CI of AE Rate with 80 subjects.

Table 16 Two-sided 95% Exact CI of AE Incidence Rate with 80 Evaluable Subjects

Number of AE	AE Incidence Rate Estimates	95% CI of Incidence Rate (%)
8	10.0%	(4.4,18.8)
16	20.0%	(11.9,30.4)
24	30.0%	(20.3,41.3)
32	40.0%	(29.2,51.6)
40	50.0%	(38.6,61.4)

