8.2.11 Extent of Exposure

Extent of Exposure for a subject is defined as number of cycles in which the subject receives the study medication infusion. Summary statistics will be provided on Extent of Exposure for ASaT population.

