3.6.2 Statistical Methods for Safety Analyses

Safety and tolerability will be assessed by clinical review of all relevant parameters including adverse experiences (AEs), laboratory tests, and vital signs by PD-L1 status within cohort and total (combining across Cohorts A-C). Summary statistics (counts, percentage, mean, standard deviation, etc.) will be provided for the safety endpoints as appropriate. The

confidence interval for the incidence rate of Grade 2 or higher adverse events with an immune etiology and the incidence rate of Grade 4/5 AEs will be provided as appropriate.

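### Primary safety objective: AE risk is planned only as subject-level percentages, although AE observation time follows time on drug; an exposure-adjusted rate should be added

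*Combined protocol and SAP*

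**What the plan says.** Protocol 3.1 makes safety and tolerability a primary objective, to be described "across cohorts and by PD-L1 status within lines of treatment for mTNBC".

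The planned measure is a proportion of subjects. Protocol 8.2.5.2 says "Summary statistics (counts, percentage, mean, standard deviation, etc.) will be provided for the safety endpoints as appropriate", and Protocol 8.1 adds that "Confidence intervals for rates of AEs of clinical interest will be computed using the exact binomial method". Table 14, "Two-sided 95% Exact CI of AE Incidence Rate with 55 Evaluable Subjects", shows what the plan means by an incidence rate: 6 of 55 subjects is 10.9%. Intervals for Grade 2 or higher immune-etiology AEs and for Grade 4/5 AEs are to be given as appropriate.

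The grouping differs between the two plans. The protocol has "laboratory tests, and vital signs by cohort and total (combining across Cohorts A-C"); sSAP 3.6.2 has "by PD-L1 status within cohort and total (combining across Cohorts A-C").

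Exposure is a separate summary. In Protocol 8.2.11, "Extent of Exposure for a subject is defined as number of cycles in which the subject receives the study medication infusion", summarised for the ASaT population with no stated breakdown by cohort or PD-L1 group. sSAP 3.11 adds days on therapy by treatment group for a population called FAS, which neither plan defines. Protocol 4.2.3.2 says AE onset and duration are recorded. Neither plan analyses them.

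**The concern.** The AE window is tied to treatment. All AEs are collected to 30 days after treatment stops (Protocol 7.2). SAEs and ECIs are collected to 90 days, or 30 if new anticancer therapy starts (7.2.3.1, 7.2.3.2). Treatment ends at confirmed progression, at 24 months, or for other listed reasons (5.8). A group that progresses later is therefore observed longer and has more chance to record an event at the same monthly risk.

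The groups named in the objective are ones for which the background leads one to expect different progression times. If that happens, a higher percentage of immune-related AEs in first-line or PD-L1 strong (+) subjects could reflect toxicity or only longer treatment, and the planned tables cannot separate the two. The A-C total would then be an average weighted by enrolment: about 205 second-line-plus subjects (160 + 45) to 80 first-line.

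**Working it through.** **1. Reproduce the plan's figures.** Exact limits for x events in n subjects are the 2.5% quantile of Beta(x, n-x+1) and the 97.5% quantile of Beta(x+1, n-x). For 6/55 this gives 4.1% to 22.2%; for 16/80, 11.9% to 30.4%. All ten intervals in Tables 14 and 16 reproduce to the printed decimal. The denominator is subjects, and time at risk does not enter. No printed figure is wrong.

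**2. Inputs for time on drug.** The documents give no time on pembrolizumab by cohort or PD-L1 group in this trial. Three pairs of medians in them can serve as proxies (1 month = 30.4375 days):
- mTNBC duration of therapy, Protocol 4.2.1: 11.9 weeks first line, 9 weeks second line (2.74 v 2.07 months).
- Chemotherapy PFS, Table 1: 5.4 months first line, 2.7 months second line.
- Pembrolizumab PFS in NSCLC, Protocol 4.1.1: 27 weeks treatment-naive, 10 weeks previously treated (6.21 v 2.30 months).

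**3. Assumptions not in the documents.** The same constant hazard h of a first event applies in both groups: 5% per month, range 2% to 8%. Time on drug is exponential with median m, capped at 24 months. The tail after treatment is w = 1 month.

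**4. Formula.** With λ = ln 2 / m, the expected crude proportion is

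1 − e^(−hw) × [λ + h·e^(−24(λ+h))] / (λ + h).

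Table 1, second line: λ = 0.693/2.7 = 0.2567. The bracket over (λ + h) is 0.8371. Times e^(−0.05) = 0.9512 this is 0.7963, so the crude proportion is 20.4%. First line: λ = 0.1284, ratio 0.7236, product 0.6883, crude 31.2%.

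| Proxy for time on drug | h = 2% | h = 5% | h = 8% |
|---|---|---|---|
| mTNBC therapy duration, 1L v 2L | 9.1% v 7.5% | 20.5% v 17.2% | 29.8% v 25.5% |
| Table 1 PFS, 1L v 2L | 14.8% v 9.1% | 31.2% v 20.4% | 42.9% v 29.6% |
| NSCLC PFS, naive v treated | 16.2% v 8.1% | 33.7% v 18.4% | 45.8% v 27.0% |

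The true hazard is equal in every cell. Cohorts A and C also take third-line and later subjects; the 4-week third-line therapy duration in Protocol 4.2.1 gives 10.8% at 5%.

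**5. Sensitivity.**
- Equal time on drug: no gap.
- A 3-month tail at 5%: 37.7% v 28.0% on Table 1 PFS (ratio 1.35, down from 1.53) and 28.1% v 25.1% on mTNBC therapy duration.
- All risk in the first 2 months, at 10% per month: 17.6% v 17.1% on Table 1 PFS.

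**6. Does a person-time rate repair it?** Under the Table 1 model at 5%, expected first events per subject over expected person-months at risk are 0.204/4.07 in second line and 0.312/6.23 in first line. Both are 5.0 per 100 person-months. By contrast, cumulative incidence at 12 months with end of the AE window as a competing event gives 19.9% v 27.8%: it is the crude proportion accrued so far and keeps the distortion.

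**The case against.** The strongest reply is that the premise is unproven. No section reports time on pembrolizumab by cohort in this trial, or by PD-L1 status in mTNBC. The proxy closest in kind, actual duration of therapy in mTNBC, gives a gap of about 3 points at 5% per month, and the result also needs a hazard that persists. Protocol 5.2.1.2 says immune-related AEs can appear soon after the first dose or months after the last, which supports no single shape. This stands, and it makes the size conditional. It does not remove the gap, because percentages cannot show which case holds.

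A second reply is that exposure is already displayed. Protocol 1.0 lists the cohorts as the treatment groups, so sSAP 3.11 can be read as days on therapy by cohort. That helps in part, but it gives no PD-L1 breakdown, uses an undefined population and is not linked to any AE rate.

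A third reply is that this is a non-randomised estimation study with no between-group safety test. True, but the objective asks for safety by these groups, and readers will compare the columns.

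A reader might go further and infer that the A-C percentage understates the risk of staying on treatment. The documents do not support that. The proportion of treated subjects with an event and the risk for someone kept on drug for 12 months are different quantities. Under the Table 1 medians only about 5% of second-line and 21% of first-line subjects would still be on treatment at 12 months.

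**Conclusion.** The concern holds in conditional form. Both SAPs answer a primary objective with subject-level proportions and exact binomial intervals, while observation time follows treatment duration. Groups with unequal time on drug are not comparable on that scale. With an identical constant hazard of 5% per month and a one-month tail, the artificial first-line v second-line difference runs from about 3 points (21% v 17%) through 11 (31% v 20%) to 15 (34% v 18%), according to the proxy. It is close to zero if risk is confined to the first two months, and zero if exposure is equal.

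It would be too strong to say that time on drug is known to differ greatly between these groups. The background (line-of-therapy PFS, and the PFS hazard ratio of 0.52 for strong v weak/negative PD-L1 in NSCLC) makes a difference plausible and no more. This is a gap in the analysis plan that should be closed.

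**What to change.** Keep the percentages and exact intervals. In Protocol 8.2.5.2 and sSAP 3.6.2:

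- For Grade 2 or higher immune-etiology AEs and for Grade 4/5 AEs, add subjects with a first event per 100 person-months at risk, with an exact Poisson interval, by cohort and by PD-L1 group within cohort. Show exposure for the same groups alongside.
- To show timing, add either the same rate by interval (for example 0-3, 3-6, 6-12 and over 12 months) or a time-to-first-event curve that censors at the end of the AE window and treats death as the competing event. Do not make end of the window a competing event.
- Use one grouping in both plans. At present the protocol splits by cohort and the sSAP by PD-L1 status within cohort.

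AE onset and duration are already recorded (Protocol 4.2.3.2), and dosing data come from Protocol 8.2.10 and 8.2.11 and sSAP 3.11. The cost is SAP wording and two more tables. The person-time rate assumes a constant hazard within each interval, late intervals may hold little person-time, and the curve assumes that subjects whose window closes would have had the same later risk as those still observed. No clinical rule changes.
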